### 3.3 Secondary analyses

#### 3.3.1 Clinician confidence (H2).

The H2 analyses, comparing clinician confidence following CI-CDS implementation to pre-implementation by treatment arm, will be carried out using all available data from PCCs who responded to either survey. Descriptive statistics will be used to characterize PCC respondents, assess the distributional properties of items from which the H2 outcomes (i.e., confidence in diagnosing and in managing CI) will be calculated and estimate clinic and PCC intraclass correlations. The distributional properties of the confidence ratings will inform how to specify the distribution and link functions for these variables (e.g., normal-identity, binomial-logit). Because ratings are unlikely to approximate a normal distribution, the anticipated H2 models are generalized LMMs to account for repeated ratings from PCCs and a link to normalize the binary outcomes:

$$\text{logit}(\text{confidence}_{it}) = \gamma_{00} + \gamma_{10}\text{CI-CDS}_i + \gamma_{01}\text{post-CI-CDS}_{it} + \gamma_{11}\text{CI-CDS}_i * \text{post-CI-CDS}_{it} + [\nu_i], \quad \text{where } i=\text{PCC}, t=\text{survey time}.$$

Parameter  $\gamma_{11}$  is expected to be positive and statistically significant, indicating more increase in confidence from pre- to post-CI-CDS implementation among PCCs at CI-CDS clinics relative to PCCs at UC clinics. Model-estimated outcomes will be calculated by treatment group and time. Change in confidence will be presented within each treatment group as an OR or RR and 95% CI. The relative OR (i.e., ROR =  $\text{OR}_{\text{CI-CDS}} / \text{OR}_{\text{UC}}$ ) and its 95% confidence interval will estimate the difference across treatment arms in change in confidence.

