Tracking CI-CDS use. Multiple processes are measured and tracked throughout the intervention period to assess CDS use as described by elements in the NIH Treatment Fidelity framework including delivery, receipt and enactment of intervention dose and content.[80] Print rates by rooming staff will be measured, grouped by clinic and clinician, and reported monthly to clinic leadership. The goal of printing the patient and clinician engagement materials will be set at $\geq 70\%$ of targeted encounters. Using this strategy, we have maintained print rates for the existing CDS engagement interfaces at over 75% for many without financial incentives. We chose 70% as the target use rate given that at any given encounter, there may be more pressing issues or psychosocial factors that should be addressed instead, such as an acute care issue or death of a spouse, and clinicians are to use their clinical judgement about when use of the CI-CDS is appropriate. If necessary, supplemental communication and training will be provided to clinics and/or clinicians who have low print rates relative to other clinics or clinicians. We will also track clinician use of online CDS features by monitoring click rates on tools, quick orders, and educational materials. However, as clinicians are encouraged to use their clinical judgement to determine when and how to use the CI-CDS tool, we will not be providing clinic- or clinician-level feedback on click rates.

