9.5.3. Secondary outcomes

H2 predicts that clinicians practicing in CI-CDS relative to UC clinics will report more post-implementation confidence in diagnosing and managing CI. We will also use a LMM approach for the H2 analyses. The distributional properties of the confidence and management composites calculated from post-implementation clinician survey data will inform how to specify the distribution and link functions for these variables (e.g., normal-identity, Poisson-log, binomial-logit, binomial-log, multinomial-cumulative logit). The fixed CI-CDS parameter and random clinic intercept from the H1 model will be retained, and a fixed parameter for the outcome value reported in the pre-implementation clinician survey will be added. Exploratory analyses will assess whether the relationship between CI-CDS and either of these outcomes is more pronounced among clinician subgroups (e.g., clinician type).

H3 predicts that patients accrued from CI-CDS clinics will have lower post-index health care utilization. Anticipating a zero-mass of patients with no emergency department or inpatient costs, we will employ a 2-part model to test H3.[86] In the first part, the probability that patients will experience one or more emergency department visits or inpatient stays will be assessed using logistic regression in the same form as was used for H1. The second part will employ a generalized linear model (GLM)[87, 88] allowing clustering by clinic and controlling for demographics and baseline risk. Such analyses often specify a gamma distribution for health care expenditures with a log link function of the explanatory variables. We will choose the distribution family based upon the data using a modified Park test and choose the link function using a Box-Cox test.[89] If we observe a statistically significant reduction in emergency department and inpatient costs in the CI-CDS group, we will use similar methods to assess whether total costs of care, including all outpatient care and pharmacy, are also lower.

Analyses of secondary and exploratory patient outcomes will also follow the same analytic approach as the H1 model with appropriate modifications to the link function and error distribution.

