## 2.2 Randomization

Simple randomization will be carried out using SAS PROC PLAN to allocate clinics equally (1:1) to the CI-CDS (intervention) or UC (control) treatment arm. Because it is common for patients to see more than one clinician in a clinic location over time, and for clinicians within a clinic location to discuss aspects of care delivery with each other, the risk of intervention contamination within clinics is rather high. Randomizing by clinic rather than by PCC or patient will minimize risk of intervention contamination.

Each accrued patient will be assigned to the clinic in which his or her index visit takes place, and as such will be assigned to the treatment group to which their clinic was randomly assigned. Post-index visits may take place in the same or different clinics or treatment groups relative to

the index visit and may or may not be eligible for the CI-CDS to offer treatment recommendations. In keeping with an ITT principle, all index and post-index visits and outcome measures for each patient will be attributed to the treatment group assignment of the clinic where the index visit took place.

The nature of the intervention prevents study personnel, clinic leaders, or primary care clinicians from being blinded to the treatment group assignment of each clinic.

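### SAP 3.3.1 tests H2 with a clinician random intercept only, although clinics are randomised, and Protocol 9.5.3 specifies a different H2 test

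*SAP*

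**What the plan says.** SAP 3.3.1 models the confidence rating with fixed effects for arm, survey time and their interaction, and a single random intercept indexed by PCC. The stated purpose is that "the anticipated H2 models are generalized LMMs to account for repeated ratings from PCCs and a link to normalize the binary outcomes". The interaction gives the ROR with a 95% interval. In addition, "Change in confidence will be presented within each treatment group as an OR or RR and 95% CI". The analysis is run "using all available data from PCCs who responded to either survey". Clinic appears only among the descriptive statistics, which will "estimate clinic and PCC intraclass correlations"; nothing says what follows from the result.

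Protocol 9.5.3 plans H2 differently. The outcome is the post-implementation rating. On the treatment and clinic terms it states: "The fixed CI-CDS parameter and random clinic intercept from the H1 model will be retained". The earlier rating then enters the model as a covariate, in these words: "a fixed parameter for the outcome value reported in the pre-implementation clinician survey will be added".

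Elsewhere the SAP does account for clinic. Section 2.2 randomises clinics, section 2.4.2.2 gives each PCC the arm of the primary clinic, the H1 model in 3.2 has a random clinic intercept, and the H3 cost model in 3.3.2 allows for clustering by clinic.

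**The concern.** There are two faults.

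First, the H2 model leaves out the randomised unit. Any tendency of PCCs in one clinic to change together is then counted as independent information, which narrows the ROR interval and the within-arm intervals. The documents give some reason to expect such a tendency. SAP 2.2 says it is common "for clinicians within a clinic location to discuss aspects of care delivery with each other". Protocol 5.4 says that, if necessary, "supplemental communication and training will be provided to clinics and/or clinicians who have low print rates relative to other clinics or clinicians".

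Second, the two documents name different tests for the same secondary hypothesis. They differ in baseline handling, in error terms and possibly in who is analysed. The SAP presents itself as an expansion of the protocol and does not say that it replaces this test. That leaves a choice open after the survey data are in hand.

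**Working it through.** **No H2 figure to reproduce.** Neither document gives a sample size, power or ICC for H2. The plan's own clinic-clustering calculation, for H1, does reproduce: 34 × 100 = 3,400 patients, design effect 1 + 99 × 0.04 = 4.96, effective sample 3,400/4.96 = 685, minimum detectable rate 19.81% against the stated 19.8%.

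**Which clinic variation matters.** Suppose a clinic contributes a stable level and a separate deviation at each survey. The stable level cancels from a PCC's post-minus-pre change, and largely cancels when some PCCs answer only one survey. The clinic-by-time deviation does not cancel. With *m* respondents per clinic and clinic ICC of change ρ, the correct interval is wider than the SAP's by √(1 + (m − 1)ρ).

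**Inputs from the documents.** 30 clinics (Protocol 9.2.2, the minimum); about 8 PCCs per clinic (Protocol 15.3: 25 in 3 pilot clinics, 25/3 = 8.3); 60% response (Protocol 6.2.5). Respondents per clinic: 8.3 × 0.6 ≈ 5.

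**Closed form, m = 5.**
- ρ = 0.03: 1 + 4 × 0.03 = 1.12; interval should be 5.8% wider; true two-sided error 6.4%.
- ρ = 0.05: 1 + 4 × 0.05 = 1.20; interval should be 9.5% wider; true error 7.4%.

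This treats every respondent as having both ratings and applies ρ to the observed change score.

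**Simulation of the anticipated logistic model, no treatment effect.** 30 clinics, 8 PCCs per clinic, 60% response at each survey, PCC random intercept fitted by maximum likelihood, Wald test at 1.96, 40,000 replicates per scenario (Monte Carlo SE about 0.1 points). Assumed latent variance shares: PCC 0.35, stable clinic 0.05; the other 0.60 is split between clinic-by-time and residual, so ρ = share/0.60. The assumed conditional intercept is −0.35. Coverage is for the change within the CI-CDS arm. Paired entries are independent responses / same PCCs answering both surveys.

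| Clinic-by-time share | ρ | Type I error, % | Coverage of 95% interval, % |
|---|---|---|---|
| 0 | 0 | 4.4 / 4.8 | 95.9 / 95.3 |
| 0.02 | 0.03 | 5.1 / 5.6 | 95.0 / 94.2 |
| 0.03 | 0.05 | 5.5 / 6.0 | 94.5 / 94.4 |
| 0.05 | 0.08 | 6.2 / 7.1 | 93.9 / 93.0 |
| 0.10 | 0.17 | 8.2 / 9.3 | 91.9 / 90.8 |

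With clinic-robust standard errors (factor J/(J − 2), t on 28 df), type I error is 4.1-4.8% and coverage 94.3-95.0% throughout.

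**Sensitivity of the SAP test at shares 0.02 / 0.05 / 0.10.** With 38 clinics: 5.1-5.9 / 6.7-7.1 / 8.7-9.2%. With 12 PCCs per clinic (assumed): 6.0 / 8.0-8.5 / 11.2-11.9%.

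**Second simulation, different settings.** 34 clinics, 8 PCCs, 60% response, PCC SD 1.3 logits, stable clinic SD 0.5 logits, 5,000 trials per scenario. For a clinic SD of change of 0 / 0.3 / 0.5 / 0.8 logits, rejection was 4.7 / 5.0 / 5.4 / 6.5% (independent) and 5.0 / 5.1 / 5.6 / 7.7% (same responders). In the last case the model's standard error was 0.524 against an empirical SD of 0.600. Clinic-clustered errors gave 4.1-5.4%.

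**Who is analysed.** With independent responses at 60%, the share with both surveys is 0.6 × 0.6 = 36%, and with either survey 1 − 0.4 × 0.4 = 84%. If the same PCCs answer both, each is 60%. The protocol model needs a pre-survey value and gives no rule when it is missing. SAP 2.4.2.2 invites PCCs to the post-survey whether or not they answered the first, so missing pre-survey values should be expected.

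**The case against.** The strongest reply is that the harm is small and its size rests on no documented quantity. At ρ of 0.03-0.05 the simulated error is within 1 point of nominal. That range is borrowed from Protocol 9.2.2 and SAP 6.0, where it describes clinic differences in the level of patient diagnosis, not in the change of clinician confidence. The larger figures need strong heterogeneity. Taking the residual variance as π²/3 = 3.29, share 0.05 gives total variance 3.29/0.55 = 5.98 and a clinic SD of change of √(2 × 0.05 × 5.98) = 0.77 logits. Clinic odds ratios for change would then span about 0.22 to 4.6 with no treatment effect. Share 0.10 gives about 1.15 logits, a span of about 0.11 to 9.5. All of this stands, and those rows are stress tests.

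The reasons to expect variation are also only suggestive. The extra training is conditional, concerns print rates, may target single clinicians, and might even out clinics. The PCC count comes from three pilot clinics, and pilot locations are excluded from the trial.

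Two further replies carry less weight. The SAP calls its models anticipated and will estimate a clinic ICC, but the flexibility it states covers distribution and link, not the random effects. The either-survey analysis set fits the SAP's open invitation to the post-survey; that explains one difference from the protocol but does not reconcile the two tests.

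Finally, the protocol's baseline-adjusted model was not simulated. The view that it is valid rests on reasoning: it has one outcome per PCC and a clinic intercept that absorbs clinic variation in that outcome.

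**Conclusion.** The point holds. H2 inference in the SAP omits the randomised unit, and the two documents specify different H2 tests. The second fault needs no assumption about variances.

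The narrowing of the intervals is conditional. It is absent if clinics differ only in a stable level, and it appears if change in confidence varies between clinics. With about 5 respondents per clinic, simulated type I error is 5.1-6.0% at an ICC of change of 0.03-0.05. The closed form gives 6.4-7.4% for the same range. At an ICC of 0.17 the simulated error is 8.2-9.3%, with within-arm coverage of about 91-92%. These ICCs, the other variance shares and the pilot-based PCC count are assumptions. H2 is secondary and H1 is not affected, so this should be corrected but does not threaten the trial's main conclusion.

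**What to change.** In SAP 3.3.1, base inference for the interaction and for the within-arm changes on the clinic: standard errors clustered by clinic (not by PCC), a small-sample correction, and clinics-minus-2 degrees of freedom.

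Two alternatives need care:
- A logistic mixed model with PCC, clinic and clinic-by-survey-time random effects is possible. In 4,000 replicates per scenario (Monte Carlo SE about 0.3 points) it was somewhat conservative (type I error 3.3-5.0%). It often put the clinic-by-time variance near zero: the SD was estimated below 0.1 in 66-67% of replicates at share 0 and in 18-21% at share 0.10.
- Adding only the H1-style clinic intercept to the SAP model would not repair the interaction test, because the uncorrected variation is clinic-by-time.

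Name the same test in Protocol 9.5.3 and SAP 3.3.1 before the survey data are analysed. If the protocol's baseline-adjusted model is chosen, state how missing pre-survey values are handled; otherwise it uses only PCCs who answered both surveys.

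The cost is wording in both documents and a wider ROR interval. In the simulation the clinic-robust standard error exceeded the SAP one by about 0 / 3 / 5 / 8-9 / 15-17% at clinic-by-time shares 0 / 0.02 / 0.03 / 0.05 / 0.10. Using 28 df adds about 4.5% to the width (2.048/1.960 = 1.045).

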6.2.5 Clinician surveys

As part of the R61 phase, primary care clinicians who practice in our 3 pilot clinics completed baseline surveys. Results of that survey are summarized in Section 15.3.

In the R33 phase, a baseline clinician survey conducted at HealthPartners (the primary effectiveness site) will serve as a pre-implementation assessment of clinician self-reports of

confidence and management of CI. A post-implementation clinician survey will be fielded 9-12 months after CI-CDS is implemented. Following extensive prior experience, HealthPartners Institute's Center for Evaluation and Survey Research (CESR) will field surveys using an initial leadership-endorsed invitation email to all practicing clinicians in the randomized clinics followed by as many as seven reminder emails over two months. Using this approach and modest monetary incentives, we expect clinician response rates of 60%.^[81]

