### 2.4.2 H2 outcome (secondary): Clinician confidence

#### 2.4.2.1 Clinician confidence definitions

Clinician confidence in diagnosing CI will be measured by a single survey item (How confident are you in your ability to diagnose cognitive impairment, including mild cognitive impairment or dementia?), followed by 5 items asking about confidence with specific components or steps of diagnosis (e.g., confidence conducting a cognitive assessment using tools like the MoCA, or distinguishing between types of dementia).

Confidence in managing CI care will be measured similarly. An overall confidence item (How confident are you in your ability to manage care for patients with cognitive impairment?) will be followed by 9 items addressing confidence in conducting specific care management activities (e.g., providing pharmacological treatment, accessing patient education materials).

The response options for all clinician confidence items will be a 4-point rating scale (not at all, a little, moderately, or very confident). Responses may be dichotomized prior to analysis (e.g., moderately or very vs. little or not at all).

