#### 2.4.2.2 Clinician survey administration

All eligible primary care clinicians practicing in all randomized study clinics will be invited to complete a pre-implementation PCC survey prior to clinician training on CI-CDS or its implementation in study clinics. Similarly, all primary care clinicians practicing in all randomized clinics approximately 8 months after CI-CDS implementation will be invited to complete a post-implementation PCC survey. The invitation to complete the post-implementation survey will not depend on having practiced at the clinic prior to CI-CDS implementation or upon completion of

the pre-implementation PCC survey. PCCs will be assigned to their primary clinic location and its randomized treatment group.

Invitations to complete each survey will be emailed to clinicians with a personalized link for completing the survey online. Reminder emails will be sent to clinicians who do not respond. An electronic gift card will be offered as a thank you for completing each survey.

Both surveys will include items to measure clinician confidence in diagnosing and managing care for CI as well as other barriers related to CI care and diagnosis. The post-implementation surveys emailed to clinicians who practice at CI-CDS clinics will include items regarding their use and satisfaction with the CI-CDS.

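### H2: the SAP tests a difference in change with a free baseline difference between randomised arms and no clinic term; a shared-baseline model with the protocol's clinic intercept would be more precise

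*SAP*

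**What the plan says.** SAP 3.3.1 gives the anticipated H2 model as a logit of confidence on arm (γ10), post-implementation time (γ01) and arm by time (γ11), with one random intercept, for the clinician. These are described as "generalized LMMs to account for repeated ratings from PCCs". The hypothesis rests on γ11, "indicating more increase in confidence from pre- to post-CI-CDS implementation among PCCs at CI-CDS clinics relative to PCCs at UC clinics", and the reported relative odds ratio "will estimate the difference across treatment arms in change in confidence". The analysis "will be carried out using all available data from PCCs who responded to either survey".

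The respondents at the two surveys need not be the same people. SAP 2.4.2.2 states: "The invitation to complete the post-implementation survey will not depend on having practiced at the clinic prior to CI-CDS implementation". It also places the first survey before CI-CDS training and implementation. On response, Protocol 6.2.5 says "we expect clinician response rates of 60" per cent. Items use a 4-point scale, and SAP 2.4.2.1 adds: "Responses may be dichotomized prior to analysis".

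Protocol 9.5.3 describes a different H2 model. The outcome is the post-implementation composite, the pre-survey value enters as a fixed covariate, and the random clinic intercept of the H1 model is kept. SAP 3.3.1 gives no reason for leaving that form. Its descriptive step will "estimate clinic and PCC intraclass correlations", but the model equation has no clinic term.

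**The concern.** With γ10 in the model, each arm's pre-implementation mean is estimated separately and subtracted. Randomisation by clinic and a survey taken before exposure give both arms the same expected baseline among eligible clinicians. Subtracting two separately estimated baselines therefore adds pre-survey sampling noise to the contrast. Partial pairing makes this worse: a clinician who answers only the second survey contributes to γ11 only after subtraction of a baseline that comes from colleagues.

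The sample is modest. The pilot found 25 eligible clinicians in 3 clinics (Protocol 15.3). At that density 30 clinics would have about 30 × 25/3 = 250 eligible clinicians and, at 60% response, about 150 respondents per survey. Neither document gives a power calculation for H2. What is at stake is the chance of missing a real gain in confidence.

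**Working it through.** There is no H2 sample size, power, variance or correlation in either document, so there is no stated figure to reproduce.

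**Inputs from the documents.** Allocation is 1:1 by clinic (SAP 2.2), with at least 30 clinics (SAP 2.1), about 8 eligible clinicians per clinic (25/3, Protocol 15.3) and 60% response (Protocol 6.2.5).

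**Assumed inputs.**
- Pre-post correlation ρ is 0.4 to 0.7.
- Clinic ICC for confidence c is 0.05 to 0.10, with the same clinic effect at both surveys.
- Three response patterns are used: complete pairs, about 5 per clinic (8 × 0.6); independent response at 60%, giving 36% both, 24% pre only, 24% post only; and more overlap, 48/12/12.

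**Step 1: variance ratio.** Let the estimated pre and post means in an arm have equal variance v and correlation R. With a free baseline the variance per arm is 2v(1−R). With a shared baseline it is v(1−R²). The ratio is 2(1−R)/(1−R²) = 2/(1+R).

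**Step 2: independent clinicians.** For a share p paired and a share a in each single-survey group, R = pρ/[p + a(1−ρ²)].
- Complete pairs: R = ρ, so 2/1.4 = 1.43 and 2/1.7 = 1.18.
- 36/24/24, ρ = 0.4: R = 0.144/0.5616 = 0.256, ratio 1.59. At ρ = 0.7: R = 0.252/0.4824 = 0.522, ratio 1.31.
- 48/12/12, ρ = 0.4: R = 0.192/0.5808 = 0.331, ratio 1.50. At ρ = 0.7: R = 0.336/0.5412 = 0.621, ratio 1.23.

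**Step 3: clinic intercept in both models.** A stable clinic effect adds c to the variance and to the covariance of the clinic's two means, so R rises.
- Complete pairs, m per clinic: R = [ρ+(m−1)c]/[1+(m−1)c]. With m = 5, ρ = 0.4, c = 0.05: 0.60/1.20 = 0.500, ratio 1.33. With ρ = 0.7, c = 0.10: 1.10/1.40 = 0.786, ratio 1.12.
- 36/24/24 of 8, ρ = 0.4, c = 0.05: the within-clinic correlation is 0.35/0.95 = 0.368. The GLS variance and covariance of the two means are 0.191 and 0.045. Then R = (0.045+0.05)/(0.191+0.05) = 0.39, ratio 1.44.

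| Pattern | ρ | Independent | c = 0.05 | c = 0.10 |
|---|---|---|---|---|
| Complete pairs, 5 per clinic | 0.4 | 1.43 | 1.33 | 1.27 |
| | 0.7 | 1.18 | 1.14 | 1.12 |
| 36/24/24 of 8 | 0.4 | 1.59 | 1.44 | 1.34 |
| | 0.7 | 1.31 | 1.24 | 1.19 |
| 48/12/12 of 8 | 0.4 | 1.50 | 1.38 | 1.31 |
| | 0.7 | 1.23 | 1.18 | 1.15 |

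**Step 4: effect on power.** A test with 80% power under the shared baseline has power Φ[(1.960+0.842)/√k − 1.960] at variance ratio k. That is Φ(0.71) = 76% at k = 1.1 and Φ(0.41) = 66% at k = 1.4.

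**Step 5: dropping the arm term without adding a clinic term.** For complete pairs, true over model-based variance is 1 + (m−1)c(1−ρ)/(1+ρ). With m = 5 this is 1 + 0.2 × 0.3/1.7 = 1.035 (ρ = 0.7, c = 0.05) and 1 + 0.4 × 0.6/1.4 = 1.17 (ρ = 0.4, c = 0.10). The same GLS calculation for 36/24/24 gives 1.07 to 1.23. Two-sided type I error is 2[1−Φ(1.960/√k)]: 5.4% at 1.035 and 7.7% at 1.23. With the arm term kept, a stable clinic effect cancels in the change, and true over model-based variance is about 0.97 to 1.00.

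**Step 6: logit scale.** The expected information of the SAP's logistic random-intercept model, without clinic effects, gives ratios of 1.62 to 1.25 for complete pairs and 1.74 to 1.40 for 36/24/24 (latent clinician ICC 0.4 to 0.8). The loss is therefore not produced by the normal approximation. The ratios with a clinic intercept were worked out on the normal scale only.

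**The case against.** The best defence of the SAP model is that a free baseline is safer here. Randomisation equalises expected baselines for all eligible clinicians, not for those who choose to answer. About 40% non-response is expected at each survey, allocation is unblinded, and neither document says that the first survey precedes clinics learning their assignment. If respondents differ by arm at baseline, the constrained model can be biased. This stands as a real but small downside, and it is why the unconstrained model should still be reported.

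A second objection is that a difference in change protects against clinic effects that the SAP model omits. That is correct, as step 5 shows, and it means the arm term cannot be dropped on its own.

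A third is that the size is unknown. That also stands: without ρ or the clinic ICC for confidence, the ratio is conditional. It moves towards 1 when ρ is near 1 and towards 2 when ρ is near 0 or few clinicians answer both surveys.

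A reader might go further and infer that the SAP test is biased, or that the missing clinic intercept by itself makes its type I error too high. The documents do not support either. The interaction is a legitimate contrast under randomisation, and with the arm term in place a stable clinic effect cancels.

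**Conclusion.** The point holds as a loss of precision for a secondary outcome, together with an unexplained departure from Protocol 9.5.3 on both baseline adjustment and clinic clustering. Under the assumed ρ of 0.4 to 0.7, clinic ICC of 0.05 to 0.10 and about 5 to 7 respondents per clinic, the SAP variance is about 1.1 to 1.4 times that of a shared-baseline model with a clinic intercept. The range of about 1.2 to 1.6 applies only if clinicians are independent, and clinic randomisation gives no ground for assuming that. Because the change uses data already being collected and follows the protocol's own intent to adjust for baseline, it is a cheap improvement and not a correction of an invalid test.

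**What to change.** Make one edit to SAP 3.3.1 with four parts:
- Constrain the pre-implementation mean to be common to both arms: remove γ10 and keep the time and arm-by-time terms. γ11 is then the baseline-adjusted post-implementation difference between arms.
- In the same edit, add the random clinic intercept already specified in Protocol 9.5.3, alongside the clinician intercept. Neither change should be made without the other.
- Keep everyone who answered either survey. The protocol's covariate form, as written, needs a pre-survey value for each clinician; the constrained model does not.
- Report the model with γ10 free, and with the clinic intercept, as a sensitivity analysis. State whether the first survey was fielded before clinics knew their assignment.

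Add a sentence explaining how this relates to Protocol 9.5.3. No new data are needed. The cost is that the main H2 result then relies on equal expected baselines among survey respondents.
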